# 4 Change to protocol specified analyses

No change from protocol specified analysis was made.

# 5 Appendix

### 5.1 Derivation of time point of treatment discontinuation

The time point of **treatment discontinuation** is the date of last dose of study medication given as study treatment but not as rescue medication, not after re-initiation or not after as initial dose after failure of 1-3 DEx cycles, and not as concomitant medication (if applicable).

For patients randomized to DEX monotherapy the time point of treatment discontinuation is the date of last study medication dexamethasone documented on the "End of Treatment" CRF. During the data review meeting it will be verified, that this date corresponds to the stop of study treatment but not to the stop of rescue medication.

For patients randomized to ETX+DEX combination therapy the time point of treatment discontinuation is the maximum date of the study medications eltrombopag and dexamethasone documented on the "End of Treatment" CRF, in general. When the primary reason for permanent discontinuation of eltrombopag is:

- "stop of eltrombopag re-initiated after relapse", or
- "stop of eltrombopag as rescue medication for patients randomized to DEX monotherapy" or
- the free text specification of "other reason" indicate that elthombopag was re-initiated or used after switch from DEX to ETB

the stop of study treatment eltrombopag has to be visually assessed from the data of the "Eltrombopag – Dosage Administration Form" during the data review meeting.

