- Screening Period: Patients will be screened based on the inclusion and exclusion criteria specified in Section 5.1 and Section 5.2, respectively.
- Treatment Period:

Arm A: Patients will be treated for 26 weeks (6 months) during the treatment period. Patients who reach platelet counts $\geq 30 \times 10^{9}/L$ and maintain counts $\geq 30 \times 10^{9}/L$ during the tapering phase will be eligible for treatment discontinuation. Duration of tapering before treatment discontinuation at Week 26 will be 6 weeks.

Arm B. Patients will be treated up to 12 weeks (3 months) during the treatment period. Patients who reach platelet counts $\geq 30 \times 10^9$ /L and maintain counts $\geq 30 \times 10^9$ /L after 1-3 cycles of dexamethasone treatment will be eligible for treatment discontinuation. Patients with platelet counts $< 30 \times 10^9$ /L after 3 cycles of dexamethasone treatment will be offered a course of eltrombopag treatment within the study and will discontinue from study at Week 52.

• Observation period: After completion of treatment period, patients will be observed for sustained response off treatment.

Arm A: Patients who successfully taper off, discontinue eltrombopag and maintain platelet counts $\geq 30 \times 10^{9}$ /L in the absence of bleeding or use of any rescue therapy will be observed until Week 52 after study start. Patients who relapse after eltrombopag discontinuation will reinitiate treatment with eltrombopag till Week 52 and will discontinue from study at Week 52. Patients with platelet counts $< 30 \times 10^{9}$ /L after 26 weeks of treatment with eltrombopag will continue eltrombopag treatment till Week 52 and discontinue from study at Week 52.

Arm B: Patients who successfully discontinue dexamethasone treatment and maintain platelet counts $\geq 30 \times 10^{9}$ /L in the absence of bleeding or use of any rescue therapy will be observed until Week 52 after study start. Patients who relapse (platelet count < 30 × 10⁹/L) after dexamethasone discontinuation and need treatment will be treated with eltrombopag until Week 52 after study start and discontinue from study at Week 52. Patients with platelet count < 30 × 10⁹/L after 3 cycles with dexamethasone will initiate treatment with eltrombopag and discontinue the study at Week 52.

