Patients who relapse (< 30×10 ⁹ /L) after eltrombopag discontinuation before Week 52	Re-initiate treatment with eltrombopag with a starting dose of 50 mg/day till Week 52 and discontinue from study at Week 52	

Treatment in the control arm consists of 1-3 cycles of high-dose dexamethasone administered orally at a dose of 40 mg QD for 4 consecutive days at 4 weeks intervals (dexamethasone can also be given at 14 to 28 days intervals if needed according to current ITP guidelines). If the platelet counts are $> 150 \times 10^{9}$ /L no further course of dexamethasone will be given. Patients will be treated up to 12 weeks (3 months) during the treatment period with dexamethasone. Patients who reach platelet counts $\ge 30 \times 10^{9}$ /L and maintain counts $\ge 30 \times 10^{9}$ /L after 1-3 cycles of high-dose dexamethasone treatment will be eligible for treatment discontinuation. Patients with platelet counts $< 30 \times 10^{9}$ /L after 3 cycles of dexamethasone treatment will be offered a course of eltrombopag treatment within the study and will discontinue the study after completion of treatment with eltrombopag at Week 52 (Table 6-2).

Table 6-2Dexamethasone dosing guidance for patients not meeting criteria for
sustained remission

Platelet Level	Dose Guidance
Patients with platelet count < 30×10 ⁹ /L after 3 cycles with dexamethasone	Initiate treatment with eltrombopag with a starting dose of 50 mg/day and continue treatment with eltrombopag till Week 52 after study start and discontinue from study at Week 52
Patients who relapse (platelet count < 30×10 ⁹ /L) after dexamethasone discontinuation before Week 52	Initiate treatment with eltrombopag with a starting dose of 50 mg/day till Week 52 after study start and discontinue from study at Week 52

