6.2.3 Rescue medication

Any ITP-directed medication or therapy, other than randomized treatment, given during the treatment phase of the trial with the aim to increase platelet count for the subjects who have clinically significant bleeding will be considered a rescue therapy and must be recorded on the appropriate eCRF page. A subject who receives rescue medication or therapy will not be considered in having achieved sustained response off treatment for the primary endpoint. Any ITP-directed medication or therapy given during the follow-up phase after treatment discontinuation until week 52 will be considered non-responders for the primary endpoint.

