#### 2.4.2 Prior, concomitant and post therapies

The FAS will be used for the analyses below.

The number of subjects using rescue treatments as defined in section 6.2.3 of the CSP will be summarized by treatment group for the periods pre-randomization, during on-treatment period and after on-treatment period. Listings will display the kind and duration of all ITP-directed pre-treatments and rescue medications separately.

For analyses of rescue medication (e. g. dose, time point, etc.) the Data Review committee decided which doses of dexamethasone, eltrombogag and other ITP-directed therapies were used as rescue medication and as study treatment. Concomitant medications (of any type, i.e. classified as rescue medication or not) and significant non-drug therapies prior to and after the start of the study treatment will be listed and summarized according to the Anatomical Therapeutic Chemical (ATC) classification system, by treatment group.

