#### 5.5 Statistical models

#### 5.5.1 Primary analysis

Proc logistic is used. The SAS code will be implemented in the TFL shells as programming note.

Rescue medication will be identified by the respective yes/no-items in the forms "Prior/Concomitant medication", "Procedures and Non-drug therapy", "WHO Bleeding Scale", "Dosage administration record for Eltrombopag", and "Dosage administration record for Dexamethasone". During the data review meeting the medication of each patient was reviewed and considered if the investigators' classification as rescue medication (yes or no) is reasonable. Unambiguous cases were overruled. For example when only the first episode but not the subsequent episodes were classified as a rescue medication by the investigator.

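### Eltrombopag after relapse is not classified alike in the two arms, so the by-arm count of rescue use can overstate the difference in favour of eltrombopag

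*SAP*

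**What the plan says.** **The step itself.** Protocol Section 3 says of Arm A: "Patients who relapse after eltrombopag discontinuation will reinitiate treatment with eltrombopag till Week 52". Table 6-1 (Section 6.1) has the matching row: "Re-initiate treatment with eltrombopag with a starting dose of 50 mg/day till Week 52 and discontinue from study at Week 52". Table 6-2 gives the same starting dose and the same end point, Week 52, to Arm B patients who relapse after dexamethasone. It has a separate row for patients still below 30 x 10^9/L after three cycles.

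**The definition of rescue.** Protocol 6.2.3 defines rescue as "Any ITP-directed medication or therapy, other than randomized treatment, given during the treatment phase of the trial", for subjects with clinically significant bleeding. For the follow-up phase it says only that any ITP-directed therapy makes the patient a non-responder. It does not say whether that therapy is called rescue.

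**The labels.** SAP 5.1 quotes two reasons for permanent discontinuation of eltrombopag: "stop of eltrombopag re-initiated after relapse" and "stop of eltrombopag as rescue medication for patients randomized to DEX monotherapy". The same section dates treatment discontinuation by the last dose "given as study treatment but not as rescue medication, not after re-initiation or not after as initial dose after failure of 1-3 DEx cycles".

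**The count.** SAP 2.4.2: "The number of subjects using rescue treatments as defined in section 6.2.3 of the CSP will be summarized by treatment group", split into the periods before randomisation, on treatment and after treatment. SAP 2.5.4 lists the number of patients receiving rescue treatment among the supportive results for the primary endpoint. On the source, SAP 5.5.1 says: "Rescue medication will be identified by the respective yes/no-items in the forms". It then names five forms and a review at the data review meeting. SAP 2.1.1 has eltrombopag or dexamethasone given additionally judged case by case as rescue or concomitant medication.

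**The concern.** A patient who relapses and is given eltrombopag has needed further treatment, whichever arm he or she was randomised to. The wording leans towards calling this rescue in the DEX arm and something else in the ETB+DEX arm. If the flags follow that wording, part of the between-arm difference in rescue use comes from the classification and not from what happened to the patients, and that part favours eltrombopag.

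The table matters more than its descriptive status suggests. After Amendment 3 about 24 patients are expected and every analysis is interpreted descriptively, so simple counts by arm are what a reader will take away. The trial is open label to investigators and to the trial team (protocol 6.4), so both the flag and its review are made knowing the arm.

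**Working it through.** **1. The places side by side.**

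| Place | Eltrombopag after relapse, DEX arm | Eltrombopag after relapse, ETB+DEX arm | Feeds the rescue count? |
|---|---|---|---|
| Protocol Tables 6-1, 6-2 | Prescribed, to Week 52 | Prescribed, to Week 52 | No |
| Protocol 6.2.3, treatment phase | Not randomised treatment, so can be rescue | Randomised treatment, so exempt | Yes, cited by SAP 2.4.2 |
| Protocol 6.2.3, follow-up phase | Non-response; not named as rescue | Non-response; not named as rescue | Unclear |
| SAP 5.1, stop reasons | Called rescue | Called re-initiated | No, used to find a date |
| SAP 5.1, list of excluded doses | First dose after DEX failure, separate from rescue | Re-initiation, separate from rescue | No, used to find a date |
| SAP 2.1.1 | Rescue or concomitant, case by case | Same, since study treatment ends at Week 26 | Yes |
| SAP 2.4.2, 5.5.1 | Yes/no item, then review | Yes/no item, then review | Yes |

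The rows do not agree. The stop reasons and the treatment-phase definition point to rescue in DEX only. The list in SAP 5.1 points to rescue in neither arm. SAP 2.1.1 allows rescue in both. It also uses re-initiation for the first eltrombopag dose after DEX failure, so that word is not confined to one arm. No row says that the two arms must be handled alike.

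**2. What size is possible.** The documents do not say how often the step occurs, so this is an illustration with assumed shares.

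Inputs from protocol 12.8.1: response 30% in DEX and 65% in ETB+DEX; about 24 patients, so 12 per arm. The plan's own figures reproduce at these rates with a continuity-corrected normal approximation: 47 per arm for 90% power (41 without the correction), and 24.3% power at 12 per arm against the stated ca. 24%.

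Non-responders:
- DEX: 1 - 0.30 = 0.70, and 0.70 x 12 = 8.4 patients
- ETB+DEX: 1 - 0.65 = 0.35, and 0.35 x 12 = 4.2 patients

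Let f_B and f_A be the assumed shares of these non-responders, in DEX and ETB+DEX, who go on to eltrombopag under the tables. The difference in this component of rescue use, DEX minus ETB+DEX in percentage points, is:
- step counted in both arms: 70 f_B - 35 f_A
- step counted in DEX only: 70 f_B
- excess from classification: 70 f_B - (70 f_B - 35 f_A) = 35 f_A

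The excess depends on Arm A alone:

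| f_A | Excess, points | Arm A patients not counted, of 12 |
|---|---|---|
| 0 | 0 | 0 |
| 0.25 | 8.75 | 1.05 |
| 0.5 | 17.5 | 2.1 |
| 1 | 35 | 4.2 |

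The last row is a ceiling and not an expectation. It needs every Arm A non-responder to receive eltrombopag under Table 6-1, none to be counted for another rescue therapy, and the data review to leave all of them out while counting DEX patients.

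**The case against.** The strongest reply is that the two labels never reach the rescue count. They are stop reasons, read with the End of Treatment form to fix a date. That form is not among the five from which SAP 5.1.1's neighbour on the primary analysis, SAP 5.5.1, takes rescue. One of the five is the eltrombopag dosing record, so a restart in Arm A can be flagged. This is correct. The labels show how the step is described; they do not decide the count.

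Second, SAP 2.1.1 ends Arm A study treatment at Week 26 and puts additional eltrombopag in either arm under the same case-by-case clause. SAP 2.4.2 and 5.5.1 describe a committee that reviewed and sometimes overruled the flags. This too is correct, and the review may have equalised the arms; its minutes are not in these documents. But the only example of overruling concerns later episodes in one patient, not comparability between arms. Case-by-case judgement with the arm known is not a written common rule.

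Third, the exemption in protocol 6.2.3 covers the treatment phase and clinically significant bleeding, whereas relapse after stopping belongs to follow-up. This limits how far that sentence can be pressed. It also means that the definition cited by SAP 2.4.2 is silent in the period where most of this eltrombopag would be given.

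Fourth, the SAP gives other views of the same events: listings of rescue by kind and duration, and mean dose for patients treated after Week 27 or Week 13. A careful reader could reconstruct the picture, though not from the count itself.

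**Conclusion.** The point stands as a minor one. The same prescribed step is described differently by arm, and nothing requires the by-arm rescue count to treat it alike. The count can therefore overstate the difference in favour of eltrombopag. Whether it does depends on data review decisions that the documents do not show. At the planning rates the excess lies between 0 and 35 points, with 35 as a ceiling.

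Three stronger readings are tempting and are not supported:

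- **That the rescue table would read 70% against 0%.** The 70% takes in every DEX non-responder, including dropouts and missing data, which SAP 2.5.3 counts as non-response. The 0% ignores other rescue in Arm A and the Table 6-1 row that leads to second-line therapy.
- **That classification doubles the apparent difference.** This follows only if equal shares of non-responders in both arms go on to eltrombopag, which no document states.
- **That the primary endpoint is biased.** A count below 30 x 10^9/L after discontinuation is already non-response, and protocol 6.2.3 makes any ITP-directed therapy in follow-up non-response in either arm. What is exposed is the rescue count and possibly the split of reasons for non-response in SAP 2.5.4.

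**What to change.** In SAP 2.4.2, 2.5.4 and 5.5.1, add one rule for both arms:

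- eltrombopag started, restarted or continued after failure or relapse under protocol Tables 6-1 and 6-2 has its own row;
- all other ITP-directed therapy is shown as rescue;
- a further row gives the total number of patients with either.

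Align the wording of SAP 5.1 and 2.1.1 so that rescue, re-initiation and first eltrombopag after DEX failure mean the same thing throughout. If the data review already applied a common rule, stating it in the SAP or the study report, with the separate row, is enough.

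The cost is SAP wording and one or two table rows, from dosing data already collected. The change concerns classification only and alters no treatment rule.

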#### 5.1.1 Derivation of exposure to study treatment

Exposure to study treatment is calculated by:

```
Date of treatment discontinuation – date of first dose + 1 day
```

It should be mentioned, that interruptions, i.e. when study treatment is restarted, are included in the exposure to study treatment.

#### 5.2 Imputation rules

#### 5.2.1 Study drug

Not applicable. Start and stop date of study drug is expected to be complete, because they are requested as mandatory and complete.

#### 5.2.2 AE date imputation

When day of start of AE is missing it is replaced by 15th.

Other parts of start date and the stop date is expected to be complete, because they are requested as mandatory and complete.

#### 5.2.3 Prior and Concomitant medication date imputation

Missing days are replaced by 15th, missing months by 6 (June).

This applies also to Procedures and Non-Drug Therapy.

#### 5.2.4 Other imputations

Start date of medical history may be replaced by 15th (day) respectively 6 (months), if necessary. Start day of bleeding is be replaced by 15th, if necessary.

#### 5.3 Selection of Adverse Events of Special Interest

AEs of special interest are defined by Novartis Case Retrieval Strategy:

- Thromboembolic events are all AEs matching the MedDRA SMQ "Embolic and thrombotic events"
- Severe cutaneous reactions are all AEs matching the MedDRA SMQ "Severe cutaneous adverse reactions"
- Pancreatitis are all AEs matching the MedDRA SMQ "Acute pancreatitis"
- Neutropenias are all AEs matching the MedDRA HLT "Neutropenias"
- Increased Bone Marrow Reticulin Formation are all AEs matching the CMQ "Increased Bone Marrow Reticulin Formation (all indications) [ETB115] (CMQ)"
- Hepatic decompensation are all AEs matching the CMQ "Hepatic decompensation (HCV only) [ETB115] (CMQ)"
- Hepatic impairment are all AEs matching the Novartis list for "All cases with historical and/or concurrent condition of hepatic diseases coded to MedDRA PTs which map to Hepatobiliary disorders (SOC) or Hepatobiliary investigations (HLGT)"
- Haematological Malignancies are all AEs matching the CMQ "Potential for Haematological changes" or the CMQ "Haematological malignancy"
- Clonal evolution are all AEs matching the PT "Clonal evolution" (10065163) or the CMQ "Clonal evolution"
- Cataract/lens disorders are all AEs matching the MedDRA SMQ "Lens disorders"

CMQs lists which lists all applicable PTs are provided by Novartis. It should be noted, that the Case Retrieval Strategy (including the CMQ lists and defined AESI) must be updated shortly before final analysis, e.g. at data base closure.

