4.5 Risks and benefits

4.5.1 Risk associated with Eltrombopag use

The risks to patients in this study may come from adverse events (AEs), adverse events of special interest (AESI) and lack of efficacy. The risk to patients in this study may be minimized by compliance with the eligibility criteria and study procedures, close clinical monitoring, safety and efficacy assessments as described in Section 8.3 and Section 8.4; and dose modifications as described in Section 6.5.

Eltrombopag is approved in more than 100 countries. The benefit risk profile of eltrombopag for the treatment of chronic ITP, HCV associated thrombocytopenia and severe aplastic anemia continues to be favorable. Important identified risks for the ITP indication include hepatotoxicity, thromboembolic events, post-therapy reoccurrence of thrombocytopenia, and cataract. Important potential risks of eltrombopag for the ITP include thrombotic microangiopathy with acute renal failure, potential for increased bone marrow reticulin formation, hematological malignancies, renal tubular toxicity, phototoxicity, potential for hematological changes, and potential for endosteal hyperostosis. The clinical benefit of the platelet count improvements by eltrombopag was demonstrated by a decrease in bleeding symptoms and a reduction in the proportion of eltrombopag-treated patients who required rescue therapy compared with patients in the placebo group. Refer to the [Eltrombopag Investigator's Brochure].

Women of child bearing potential and sexually active males must be informed that taking the study treatment may involve unknown risks to the fetus if pregnancy were to occur during the study, and agree that in order to participate in the study they must adhere to the contraception requirements outlined in the exclusion criteria. If there is any question that the subject will not reliably comply, they should not be entered or continue in the study.

Hepatotoxicity:

Eltrombopag administration can cause hepatobiliary laboratory abnormalities, severe hepatotoxicity, and potentially fatal liver injury. In clinical studies of adult and pediatric patients (aged 1 to 17 years) with chronic ITP who received eltrombopag, increases in serum alanine aminotransferase (ALT), aspartate aminotransferase (AST) and indirect bilirubin were observed. Exercise caution when administering eltrombopag to patients with hepatic disease.

Thrombotic/thromboembolic complications:

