12.8 Sample size calculation

12.8.1 Primary endpoint

This trial is intended to estimate the difference in the rates of patients achieving a sustained response off treatment at Week 52.

(sustained response off treatment = maintain platelet $\geq 30 \times 10^9/L$ after treatment discontinuation in the absence of bleeding events \geq Grade II or use of any rescue medication at all visits until Week 52)

The sample size calculation is based on the following assumptions:

- 1. Sustained response off treatment is achieved in 30% of the patients in the dexamethasone arm and 65% in the eltrombopag + dexamethasone arm
- 2. Randomization is allocated in a 1:1 ratio (eltrombopag + dexamethasone: dexamethasone)
- 4. A two-sided 5% level of significance will be applied.
- 5. The study will have 90% power under the stated assumptions for the primary endpoint.

Based on these assumptions, a total of 47 patients in each treatment arm would need to be randomized. More conservative scenarios based on lower treatment effects and 50 patients per group, assuming rates of 30 versus 60% would lead to a power of 81%, and 30 versus 55% would still allow for a power of 64%, whereas the radius of the respective confidence interval would be between 0.20 and 0.21 based these scenarios.

To allow for some dropouts / protocol violations, a total of 106 patients is planned to be enrolled.

Due to feasibility reasons, resulting in a substantial delay in recruitment, as described above, with Amendment 3 recruitment will be prematurely discontinued. A final number of ca. 24 patients is expected to be recruited by the time of approval.

The patients enrolled by then will be analyzed and reported as described, to allow for adequate use of the present data.

Based on the assumptions described, the resulting power will be ca. 24%. As a consequence, all analyses will be performed in a purely descriptive manner.

13 Ethical considerations and administrative procedures

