#### 2.8.1 Adverse events (AEs)

Only treatment-emergent AEs are included in the the safety analysis. Non-treatment emergent AEs are listed only in the Patient Data Listings (section 16.2.1 of the CSR).

Treatment-emergent adverse events (TEAE) are defined which started during the on-treatment period or increased in severity based on preferred term). The on-treatment period lasts from the

date of first dose of study treatment with eltrombopag or dexamethasone (whichever is first) to 30 days after the date of the last dose of study treatment (whichever is last).

The number (and percentage) of subjects with treatment-emergent adverse events will be summarized in the following ways:

- by treatment, primary system organ class and preferred term.
- by treatment, primary system organ class, preferred term and maximum severity (based on CTCAE grades).
- by treatment, Standardized MedDRA Query (SMQ) and preferred term

Separate summaries will be provided for study medication related AEs, death, SAEs, AEs leading to discontinuation and adverse events leading to dose adjustment.

The number (and proportion) of subjects with AEs of special interest (i.e. thromboembolic/ thrombotic complications, hepatobiliary laboratory abnormalities, bleeding, bone marrow reticulin formation and bone marrow fibrosis, and ocular changes) will be summarized by treatment.

A subject with multiple AEs within a primary system organ class is only counted once towards the total of the primary system organ class.

A subject with multiple AEs within a preferred term is only counted once towards the total of the preferred term class.

The incidence of AESIs will be summarized by SOC and Preferred Term (PT). In addition to the above mentioned analysis this analysis counts each AESI (which may occur multiple in one patient) but not only the occurrence in one patient/one SOC/one PT.

All deaths (on-treatment and post-treatment [starting at day 30+1 after last dose of eltrombopag]) will be summarized.

All AEs, deaths and SAEs will be listed and those collected during the pre-treatment (from day of patient's informed consent to the day before first dose of study treatment) and post-treatment period will be flagged.

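### SAP 5.3 counts events from the haematological-changes query under the heading Haematological Malignancies, although the protocol treats the two as separate risks

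*SAP*

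**What the plan says.** SAP 5.3 lists the AESI groups and the query that retrieves each. For one of them the rule is: "Haematological Malignancies are all AEs matching the CMQ 'Potential for Haematological changes' or the CMQ 'Haematological malignancy". The two queries are joined by an *or*, and the result carries the name of the second. No other row in SAP 5.3 uses the haematological-changes query or reports that concept.

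Protocol 4.5.1 sets out the important potential risks of eltrombopag in ITP. Its list includes "hematological malignancies, renal tubular toxicity, phototoxicity, potential for hematological changes, and potential for endosteal hyperostosis". Malignancies and haematological changes are separate entries, with two unrelated risks between them.

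On the content of the queries, SAP 5.3 says only that "CMQs lists which lists all applicable PTs are provided by Novartis". It adds that the retrieval strategy, "including the CMQ lists and defined AESI) must be updated shortly before final analysis, e.g. at data base closure".

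SAP 2.8.1 describes two AESI displays. One is by treatment: "The number (and proportion) of subjects with AEs of special interest (i.e. thromboembolic/ thrombotic complications, hepatobiliary laboratory abnormalities, bleeding", and the list then continues with marrow reticulin and fibrosis and with ocular changes. The other is by term: "The incidence of AESIs will be summarized by SOC and Preferred Term (PT"), and it counts every event, not only affected patients.

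**The concern.** A retrieval rule decides which events are counted under which name. Here the name is narrower, and much graver, than the rule. A reader who sees a count beside Haematological Malignancies will take it as a number of cancers. Active malignancy is an exclusion criterion (Protocol 5.2, criterion 13), so the reader will also take those cancers as new on study. If the changes query holds any non-malignant term, a patient with only that event adds to the count.

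There is a second, quieter loss. The protocol names haematological changes as a potential risk in its own right, but the SAP gives it no count. The merged row answers neither question cleanly: it can overstate malignancies, and it does not show how often haematological changes occurred.

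**Working it through.** The plan states no figure to reproduce, so the check is a comparison of texts, followed by one line of arithmetic for scale.

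**1. What the rule counts.** Let M be the patients matched by the malignancy query and C those matched by the changes query. The SAP 5.3 rule gives

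group count = number in (M or C) = number in M + number in C but not in M.

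The first term is what the heading promises. The second is the excess. It is never negative, so the group count can be too high for malignancy but never too low. Every patient in M is included, so no malignancy found by its own query is lost.

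**2. Whether the excess can be more than zero.** This depends on whether the changes query holds terms outside the malignancy query. The term lists are not in the documents, so it cannot be checked term by term. Two facts suggest that it does: the query's name, and the separate entry in Protocol 4.5.1, which would have little purpose if both risks covered the same events. This is an inference.

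**3. Whether the SAP catches such events elsewhere.** Neutropenias, increased marrow reticulin and clonal evolution each have their own row in SAP 5.3. Haematological changes do not. The SAP therefore separates neighbouring concepts elsewhere but merges these two.

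**4. Where the excess would show.**

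| Display | Effect of the merged rule |
|---|---|
| Group heading and group count | Includes any event matched only by the changes query |
| AESI summary by SOC and PT (SAP 2.8.1) | The reported term appears as itself |
| SAE summary (SAP 2.8.1) | Unaffected; Protocol 10.1.2 has malignant neoplasms assessed as serious, apart from progression of the study indication |
| Listings of all AEs and SAEs (SAP 2.8.1) | Unaffected |

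**5. Scale.** Protocol 12.8.1 states: "A final number of ca. 24 patients is expected to be recruited by the time of approval". With 1:1 allocation that is 24 / 2 = 12 per arm. One patient matched only by the changes query would add 1/12 = 8.3 percentage points to the group proportion in that arm. With no such patient the addition is 0. The figure applies only if a patient proportion is tabulated for this group. The patient-level sentence in SAP 2.8.1 does not name haematological malignancy among its categories, although SAP 5.3 defines the group.

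**The case against.** The strongest reply is that little harm can follow. The terms remain visible by SOC and PT, all events are listed, and a treatment-emergent malignancy would also enter the SAE summary. In a trial of about 24 patients, anyone could trace an entry in minutes. A broad query is a defensible way to screen for a serious outcome, and over-inclusion is the safer direction. The AESI definitions are in any case due for an update before the final analysis.

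Most of this stands, and it sets the limits of the point. A reader might infer from the merged rule that a true malignancy could not be told apart from a benign blood-count change. The documents do not support that, because the displays just named separate them. A reader might also infer that blood-count changes will certainly be reported as cancers. That goes too far, since the term lists are unseen and no such event may occur. Nor do the documents say that this table feeds a pooled product safety record; SAP section 1 limits the SAP to this study.

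Two parts of the reply do not remove the problem. Broad retrieval justifies the query but not the name given to its result. And the planned update is not described as changing this grouping, so the rule stands as written unless someone amends it.

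**Conclusion.** The grouping rule in SAP 5.3 is wrong as written, in a limited way. It puts two risks that the protocol separates under the name of the graver one, and leaves the other without a count. The error is over-inclusion at the level of the group heading and group count. Efficacy results, term-level safety rows, the SAE summary and the listings are not affected.

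The conflict between the rule and the protocol's risk list follows from the text alone. Any actual miscount rests on an assumption: that the changes query holds at least one term outside the malignancy query and that at least one patient has such an event. The number affected is unknown. The 8.3% per patient is an illustration that assumes 12 patients in the arm and a tabulated group proportion; it is not a prediction.

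**What to change.** When the Case Retrieval Strategy is updated before the final analysis, split the entry in SAP 5.3:

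- Haematological malignancies: events matching the malignancy CMQ only.
- Potential for haematological changes: events matching its own CMQ, as a separate AESI row.

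An equally good alternative is to keep the combined retrieval, give it a name that covers both concepts, and show malignancies on a row of their own beneath it.

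Either version costs one changed line in the SAP and one more table row. It needs no new data and alters no efficacy analysis or clinical procedure.
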